**Study Title:** Impact of Decision Aids in Urogynecology

**Document Title:** Design and Analysis plan for a study examining the impact of decision aids in Urogynecology

**PI:** [name] ([[contact]](mailto:[contact]))

**Statistician:** [name]

**Co-Investigators and Study team:** [name] (MGH), [name] (MGH), [name] (MGH), [name] (MGH)

**ClinicalTrials.gov:** NCT04369404

**Date:** June 5, 2023

*Background:*

Pelvic floor disorders including pelvic organ prolapse (POP), stress urinary incontinence (SUI), and overactive bladder (OAB) are significant source of impaired quality of life, psychosocial distress, and financial burden. Patients with these conditions broadly desire symptom improvement and a better understanding of their condition and treatment options.

*Purpose:*

To examine the efficacy and acceptability of decision aids (DAs) in counseling urogynecology patients with prolapse, stress urinary incontinence, or refractory overactive bladder.

*Design*

A before-after study first enrolled patients into a control group that underwent usual care without a DA. Then, the study enrolled patients in the intervention group, where providers utilized a DA for counseling. Post-visit patient surveys assessed treatment preference, knowledge, and patient-physician collaboration using SURE, CollaboRATE, and Shared Decision Making (SM) Process scales. Post-visit provider surveys assessed perception of the decision-making process and visit length. Independent t-tests were used for continuous variables (Knowledge and SDM Process scores) and Chi-square for categorical variables (treatment preference, SURE, and CollaboRATE).

*Materials:*

The three decision aids used for this study focused on POP, SUI, and OAB. The DAs were created by the Health Decision Sciences Center (HDSC) and Female Pelvic Medicine and Reconstructive Surgery (FPMRS0 faculty at Massachusetts General Hospital (MGH). These DAs were reviewed by experts at the Blum Family and Learning Center at MGH for plain language and clarity. The DA worksheets are short, paper-based forms designed to support SDM in a clinical encounter to present treatment options, and to discuss risks and benefits of each treatment option. The main feature of these one-page worksheets is the decision matrix in the middle of the page, listing four common treatment options down the left-hand side, as well as a brief explanation of the treatments' benefits, risks, and next steps. This format allows patients to visually see the pros and cons of each treatment and allows them to select an option that most closely aligns with their values.

*Sample:*

We conducted a before-after pilot study enrolling patients from the FPMRS division of the Obstetrics and Gynecology department at MGH, located in Boston, Massachusetts. Eligible patients were 18-95 years old, with POP, SUI, or OAB, and preferred language English. Patients were ineligible if they had prior surgery for POP or incontinence or if they did not attend the visit.

*Intervention:*

The intervention group, providers had access to the DA worksheets for their routine office visits and utilized the DA with the patient. In the control arm, the providers did not utilize the DAs.

*Survey protocol:*

The survey was given between February 2019 and April 2019. Participants were asked if they would be interested in participating in a research study. Then, they reviewed an information sheet that described the study and had to acknowledge that they read it and were willing to continue to the survey. Then, they continued to the survey. They were asked to complete the survey either after the visit in the waiting area or returning it in a self-addressed envelope to the research team.

*Risk and Adverse Events:*

No diagnosis or treatments were offered or administered as part of this study. The standard of care is that physicians discuss appropriate treatment options, including their benefits and risks. There are minimal risks associated with participating in the survey. No confidential or PHI was collected as part of this study.

There are no adverse events expected for this minimal risk survey study. Study staff will review the completed data set and will notify the site PI about any serious or moderate potential adverse events (AEs) immediately and any minor or potential ones at weekly meetings. The PI will review AEs individually real-time and in aggregate on a weekly basis at team meetings. The PI and clinician co-investigators will review potentially serious adverse events (SAEs), as soon as they are discovered. The PI ensures all protocol deviations, AEs, and SAEs are reported to the IRB according to the standard requirements.

There are no formal stopping rules for this minimal risk study.

*Outcomes:* The survey collected the following information:

*Measures:*

*Patient Post-Visit Survey:* the patient post-visit surveys aimed to capture several key parameters regarding the treatment choice and decision-making process between the patient and provider:

- *Knowledge questions:* Four to five multiple choice questions about the condition, treatment options, benefits, and harms. One point was given for each correct item. A total knowledge score was calculated for all respondents who completed at least half of the items. The knowledge questions on each DA were tailored to each specific condition of either POP, SUI, or OAB.
- *Treatment preference:* One items assessed the patient's preferred treatment
- *SURE scale:* A 4-item short form of the Decisional Conflict Scale measures patients' internal beliefs about (1) feeling informed, (2) clear about personal values, (3) sure about the best choice, and (4) supported in decision making. A top score is defined by responding yes to all four items.
- *CollaboRATE:* A three-item process measure of patient's perceptions of the quality of their provider's communication. The three items address whether the patient's provider understands their health issue, listens to them, and includes what matters most to them in choosing what to do next. Each item is scored on a scale of one to ten with one indicating

no effort was made by the provider and ten being every effort was made by the provider. A top score is defined by scoring ten on all three questions on the survey.

- *SDM Process scale:* A four-item measure that assess discussion of options, pros, cons, and preferences. A total score is calculated according to established scoring guides and ranges from 0-4, with higher scores indicating more shared decision making. Scores have been related to increased patient satisfaction with treatment outcomes and current symptoms, decreased decisional regret, and higher quality of life and symptoms scores.

*Provider Post-Visit Surveys:* Assessed clinicians' perceptions of patient knowledge, involvement in the decision-making process, length of visit, perception of patient satisfaction, and each provider's own satisfaction with the visit.

*Sample Size:* There was no formal power calculation done for this pilot study.

*Statistical Methods:*

This pilot study assessed the feasibility of incorporating DAs into the clinical visit and differences in the decision-making metrics between the groups. We examined efficacy by comparing the intervention and control groups on measures of knowledge scores, SURE top cores, CollaboRATE top scores. We examined acceptability of the intervention by looking at the usage of the DAs, clinicians' satisfaction with the visit, and perceptions of length of visit. Differences between cohorts were examined using independent t-test (2-sided) for continuous variables and Fisher's Exact (2-sided) test for categorical variables. The data from the intervention group was analyzed with an intention-to-treat analysis.

*Data Sharing:*

We are committed to making resources and data from the proposed research available to other investigators in the research community. The study team will create a complete, cleaned, de-identified copy of the final data set. We will also make information necessary to interpret the data, such as study protocols, data dictionaries, decision aid worksheets, and surveys available to interested investigators. Information for investigators interested in using this data will be made available on the Health Decision Sciences Center website and in publications of the data or by contacting the PI. The PI will share a de-identified data set with outside investigators at no cost, according to approved Mass General Brigham policies for data sharing. Investigators from other sites will be able to request the data and will be required to complete a data use agreement that ensures that all local IRB requirements are met before using the data, that they will not attempt to identify any data in the dataset, and that they will not share the data set with anyone outside their project team.

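### Treatment preference is tested between sequential cohorts without stratifying by condition, so a change in condition mix could pass for a change in preference

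*Combined protocol and SAP*

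**What the plan says.** - **Test.** Design groups preference with two other outcomes: "Chi-square for categorical variables (treatment preference, SURE, and CollaboRATE". Statistical Methods gives a different test: "Differences between cohorts were examined using independent t-test (2-sided) for continuous variables and Fisher's Exact (2-sided) test for categorical variables". Neither section mentions stratification, per-condition tables or adjustment for condition.
- **Population.** Sample: "Eligible patients were 18-95 years old, with POP, SUI, or OAB, and preferred language English".
- **Worksheets.** Materials: "The three decision aids used for this study focused on POP, SUI, and OAB". The matrix on each is described as "listing four common treatment options down the left-hand side". The options are not named, and nothing says whether any are shared across conditions.
- **Outcome.** Measures: "One items assessed the patient's preferred treatment". No response categories or recoding are given.
- **Tailoring.** Measures states it for knowledge only: "The knowledge questions on each DA were tailored to each specific condition of either POP, SUI, or OAB".
- **Cohorts.** Design describes a control group enrolled first and an intervention group enrolled afterwards. Nothing holds the condition mix constant between them.

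**The concern.** SURE and CollaboRATE top scores are yes/no outcomes that mean the same thing in every condition. Preferred treatment probably does not: if each worksheet offers options for its own condition, the answers open to a patient depend on her diagnosis. The distribution of preference over a whole cohort is then the product of condition mix and choice within condition.

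In a before-after design the mix can drift between periods. A pooled test responds to that drift as readily as to a real change in choice. If options with similar names are merged to avoid this, a move toward an option in one condition can offset a move away from it in another. The risk is a reported effect of the decision aid on preference that only reflects who attended clinic, or a real effect that goes unseen.

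**Working it through.** The documents give no cohort sizes, condition mix, preference rates or significance level, so there is no stated figure to reproduce. Everything below is illustration under stated assumptions.

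**Inputs from the documents:** 3 conditions, 3 worksheets, 4 options each, 2 non-randomized cohorts. **Assumed:** options distinct across conditions, two-sided 5% level, equal cohort sizes *n*, and the condition shares shown.

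**1. What a pooled table tests.** There are 3 × 4 = 12 categories in 2 cohorts, so 12 − 1 = 11 degrees of freedom. Comparing options within condition uses 3 × (4 − 1) = 9. The remaining 11 − 9 = 2 compare the condition mix, which is not preference.

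**2. Large-sample size of the effect, with no preference change.** Let the condition shares be p and q in the two cohorts. Preferences within condition are equal in both cohorts, so they drop out and the noncentrality is n × Σ (p − q)²/(p + q).

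- 50/30/20 versus 30/30/40: 0.04/0.8 + 0 + 0.04/0.6 = 0.1167. Times 25, 50 and 100 this gives 2.92, 5.83 and 11.67. Rejection on 11 df: 15.5%, 30.0% and 60.4%.
- 50/30/20 versus 40/30/30: 0.01/0.9 + 0 + 0.01/0.5 = 0.0311. This gives 0.78, 1.56 and 3.11. Rejection: 7.3%, 10.0% and 16.4%.

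**3. Small-sample correction.** With 25 per cohort over 12 categories the average expected count is 25/12 ≈ 2.1, so the approximation is poor. The same scenarios were simulated with the Pearson test, degrees of freedom taken from non-empty categories, and assumed within-condition preferences. The simulated figures are the ones to use.

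| Condition shares | n per cohort | Approximation | Simulated, pooled |
|---|---|---|---|
| 50/30/20 v 30/30/40 | 25 | 15.5% | about 10% |
| | 50 | 30.0% | about 26% |
| | 100 | 60.4% | about 60% |
| 50/30/20 v 40/30/30 | 25 | 7.3% | about 4% |
| | 50 | 10.0% | about 8% |
| | 100 | 16.4% | about 16% |

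The stratified test (within-condition chi-squares and degrees of freedom summed) rejected in about 4–6% of runs in these scenarios. Simulated values move by about a percentage point with the preference pattern assumed.

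**4. Equal mix, no preference change.** Pooled tests rejected in 3–5% of runs at 30 to 200 per cohort. Without a shift in mix, pooling does not inflate error.

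**5. Equal mix, real change.** Assumed preferences moved from .4/.3/.2/.1, .1/.2/.3/.4 and .25 each to .2/.3/.3/.2, .3/.2/.2/.3 and .45/.25/.15/.15. Power:

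| n per cohort | Pooled, 12 categories | Merged, 4 categories | Stratified |
|---|---|---|---|
| 30 | 12% | 7% | 16% |
| 50 | 27% | 9% | 31% |
| 100 | 62% | 13% | 67% |
| 200 | 95% | 23% | 96% |

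The merged version loses most of its power because the shifts partly cancel. The 12-category version loses little.

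**6. Merged options under a mix shift.** With shares .50/.25/.25 versus .30/.35/.35 and no preference change, the merged 4-category test rejected in 6%, 8%, 11% and 17% at 30, 50, 100 and 200 per cohort. Merging reduces the false signal from the mix but does not remove it.

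**The case against.** The strongest reply is that pooling is inferred from silence. The plan names a test; it does not say that the three conditions go into one table, and it leaves open a recoding or a per-condition tabulation. Condition-specific options are also inferred, since tailoring is stated only for the knowledge items. Both points stand. Even so, a single between-cohort test with no stratification is most naturally read as pooled, and three separate worksheets make different options likely.

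A reader might go further and infer that the categories share no common scale, so a pooled result cannot show whether the decision aid changed preference. The documents do not support that. A nominal test needs no scale, a common recoding is not excluded, and with an equal mix the 12-category test kept its error rate and had 62% power against 67% stratified at 100 per cohort. The loss from spreading an effect over 11 degrees of freedom is small; the exposure comes from case mix and from merging.

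Two further limits stand. At 25 per cohort under the smaller mix shift there is no inflation (about 4%). And no rejection rate was computed for Fisher's Exact, the test in Statistical Methods. It tests the same pooled hypothesis and so responds to mix as well, but the rates shown are for the Pearson test.

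Finally, the study is a pilot without a power calculation, and Statistical Methods names knowledge, SURE and CollaboRATE as the efficacy comparisons, not preference. That lowers the stakes. It does not remove the point, because Design commits to testing preference.

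**Conclusion.** The concern holds as a weakness in the analysis method. Followed as written, an unstratified test of preference in this before-after study can mistake a change in condition mix for a change in preference. The false-positive rate runs from no inflation (small shift, 25 per cohort) to about 60% (20-point shifts in two conditions, 100 per cohort), against about 5% when stratified. If options are merged, opposite shifts can cancel: 13% power against 67% in the example at 100 per cohort.

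This rests on options that differ by condition, on a mix that differs between cohorts, and on assumed sizes and shares. None of these is given in the documents. The practical consequence is modest, because preference is a secondary comparison in an unpowered pilot.

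**What to change.** Define the response categories of the preference item for each condition, and make the cohort comparison conditional on condition:

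- Give a cohort-by-option table with an exact test within each of POP, SUI and OAB, labelled descriptive.
- If one overall statement is wanted, use a condition-stratified exact test in place of the pooled test: a generalized Cochran-Mantel-Haenszel test, or one on a common binary defined before the tables are examined.
- Report the condition mix of each cohort beside the result.
- Name one test for categorical outcomes, since Design and Statistical Methods differ.

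The cost is SAP wording and a re-tabulation of data already collected, provided each respondent's condition was recorded. The downsides are real. Cells within a condition will be small; exact tests protect validity there but do not restore power. Three tests replace one. A Cochran-Mantel-Haenszel test on a common coding is still weak against opposite shifts, so the stratified power shown above, which comes from summed within-condition chi-squares, does not carry over to it. A common binary also combines different treatments, so the within-condition tables should be shown with it.

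### Knowledge totals from three condition-specific forms are compared between sequential cohorts with no condition term, so a difference in case mix can pass for a difference in knowledge

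*Combined protocol and SAP*

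**What the plan says.** The Measures section describes the knowledge outcome as "Four to five multiple choice questions about the condition, treatment options, benefits, and harms", scored so that "One point was given for each correct item". It adds: "The knowledge questions on each DA were tailored to each specific condition of either POP, SUI, or OAB". It does not say which conditions have four items and which have five, or whether totals were converted to percent.

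The Design section gives the order of enrolment: "A before-after study first enrolled patients into a control group that underwent usual care without a DA"; the intervention group followed. The Sample section admits all three conditions ("Eligible patients were 18-95 years old, with POP, SUI, or OAB, and preferred language English") and mentions no quota or matching by condition.

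For the analysis, the Design section says "Independent t-tests were used for continuous variables (Knowledge and SDM Process scores"). Statistical Methods names knowledge first among the efficacy measures and repeats the two-sided independent t-test. No condition covariate, stratified or per-condition analysis, or table of condition by cohort appears anywhere. On sample size: "There was no formal power calculation done for this pilot study".

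**The concern.** A patient's condition determines which questions she answers and may determine her maximum score. Patients were not randomised, so nothing in the design balances the three conditions between cohorts. A t-test on the total treats a point on one form as equal to a point on another. If the later cohort holds more patients whose form yields higher totals, it scores higher even if the decision aid taught nothing. If it holds fewer, a real gain can be hidden.

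Condition is also a confounder the team can remove, because the form a patient completed identifies it. Leaving it in weakens an efficacy comparison for no gain.

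**Working it through.** The plan states no sample size, case mix, score distribution or alpha, so it has no figure to reproduce. From the documents come the form lengths (4 and 5 items), one point per correct item, the order of enrolment and the two-sided t-test. Everything else below is assumed: alpha 0.05; 20, 40, 60 or 100 patients per cohort; the proportion correct on each form; and the shift in mix. Results separated by slashes follow those four cohort sizes.

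**Bias with no decision-aid effect.** The expected difference in mean total is the sum over conditions of (share in intervention cohort − share in control cohort) × (mean total on that form). For a shift *s* from four-item to five-item forms, with proportions correct *p4* and *p5*, this is *s* × (5·*p5* − 4·*p4*):

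- All forms 70% correct: 0.10 × (3.50 − 2.80) = 0.07 points; 0.20 × 0.70 = 0.14 points.
- Four-item forms 65%, five-item forms 75%: 0.20 × (3.75 − 2.60) = 0.23 points.
- Reversed (75% and 65%): 0.20 × (3.25 − 3.00) = 0.05 points.
- Equal mix (*s* = 0), or equal form means (4 × 0.75 = 5 × 0.60 = 3.0): no bias.

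For scale, the SD on a single form at 70% correct is √(4 × 0.7 × 0.3) = 0.92 or √(5 × 0.7 × 0.3) = 1.02 points.

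On percent correct the length term drops out and the bias is *s* × (*p5* − *p4*). A 10-point difficulty gap with a 20-point shift gives 0.20 × 10 = 2 percentage points.

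**Rejection rate with no true effect** (40,000 simulated studies per scenario, binomial item scores):

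| Correct on 4-/5-item form | Shift in 5-item share | t-test, raw total | t-test, percent correct |
|---|---|---|---|
| 70% / 70% | 0 points | 5/5/5/5% | about 5% |
| 70% / 70% | 10 points | 6/6/7/8% | about 5% |
| 70% / 70% | 20 points | 7/9/11/16% | about 5% |
| 65% / 75% | 10 points | 6/7/9/11% | 5–6% |
| 65% / 75% | 20 points | 10/15/20/31% | about 6/7/8/10% |
| 75% / 65% | 10 points | 5/5/5/5% | 5–6% |
| 75% / 65% | 20 points | 5/6/6/7% | about 6/7/8/10% |

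A linear model of percent correct on cohort and form rejects 4.7–5.2% in every null scenario.

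**Power for a true gain from 65% to 75% correct** (three conditions, one with a five-item form; 20,000 runs):

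| Share with the 5-item form, control to intervention | t-test, raw total | Percent correct, adjusted for condition |
|---|---|---|
| Equal | 27/48/65/86% | 27/51/68/89% |
| 40% to 30% | 20/36/50/72% | 27/51/68/88% |
| 30% to 40% | 34/60/77/94% (inflated by bias) | 27/51/68/89% |

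**Chance imbalance.** With a true five-item share of 40% in both cohorts, an observed difference of at least 10 points arises in 63/42/31/17% of studies. The t-test's sampling variance already covers this, so it does not raise the overall error rate. It does displace the raw difference in that particular study by 0.07 points or more when forms are 70% correct.

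**The case against.** The strongest reply is that the bias needs two things the documents do not show: a systematic difference in mix, and different mean totals on the forms. "The survey was given between February 2019 and April 2019", in one division, and no reason for the mix to drift in so short a time is apparent. At the more plausible 10-point shift the excess is small (6–8% with equal difficulty), and with difficulty reversed there is none. That stands: the documents show a risk, not that bias occurred.

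Second, the larger figures assume raw totals. The scoring text points to a raw sum but does not rule out percent correct, under which rejection stays at 5–6% for a 10-point shift. That also stands. It reduces the size but does not remove the problem, since percent scoring leaves the difficulty component.

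Third, pooling of the three conditions is inferred from the absence of any stratified analysis; the Sample section itself gives only eligibility. The inference is reasonable, because a single t-test on knowledge is all that is described.

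Finally, this is a non-randomised pilot, and a condition term cannot make it causal: provider, severity and time confounding remain. True, but the plan uses knowledge to examine efficacy, and this component is cheap to remove.

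**Conclusion.** The concern holds, as a conditional risk that should be fixed. An unadjusted t-test on condition-specific totals is biased if both the condition mix and the mean form scores differ, unless the contributions of the conditions happen to cancel; the direction cannot be known from the documents. On the assumed inputs the size runs from nothing (equal mix, or equal form means) through 0.07 points and 6–8% rejection (10-point shift, equal difficulty) to 0.23 points and 10–31% (20-point shift, five-item forms also easier). These rates rest on assumed cohort sizes, mix and difficulty, and on binomial scores. Patient-to-patient variation in knowledge would widen the spread and bring the rejection rates nearer 5%, without changing the bias in points. Confidence is medium, because neither the actual mix nor the scoring scale is reported.

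**What to change.** Compare cohorts on knowledge with a linear model containing cohort and condition (prolapse, stress incontinence, overactive bladder), or stratify by condition. Use percent correct on the patient's own form as the outcome so that the adjusted difference has one unit. State the number of items on each form and the denominator for the percentage. The rule admitting respondents with at least half of the items completed leaves open whether unanswered items count as incorrect, so this must be said. Report condition mix and mean percent correct by condition in each cohort. The unadjusted t-test can stand beside the adjusted result. If results are already known, label the adjusted analysis post hoc. If totals were already converted to percent, say so and add only the condition term.

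The cost is one model on survey data already held and two degrees of freedom. Against unadjusted percent correct, with three equally difficult forms, power goes from 29/52/69/89% to 27/51/68/89% with equal mix, and from 29/52/71/90% to 27/49/68/88% with a 20-point shift: a loss of up to 3 points. If difficulty differs by condition (55/70/75% correct) and mix is equal, adjustment raises power from 28/49/67/87% to 30/54/73/91%.

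### Does leaving the SDM Process scale out of both the efficacy and the acceptability lists make the efficacy analysis inconsistent?

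*Combined protocol and SAP*

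**What the plan says.** The combined protocol and SAP deals with SDM Process in several places.

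- **Design** names it with knowledge as a continuous outcome: "Independent t-tests were used for continuous variables (Knowledge and SDM Process scores". The three remaining patient outcomes get a different test: "Chi-square for categorical variables (treatment preference, SURE, and CollaboRATE".
- **Materials** describes the worksheets as "short, paper-based forms designed to support SDM in a clinical encounter".
- **Measures** defines the scale as four items with a total from 0 to 4, "with higher scores indicating more shared decision making".
- **Statistical Methods** opens by giving the pilot two tasks, one being feasibility and the other "differences in the decision-making metrics between the groups". The efficacy sentence follows: "We examined efficacy by comparing the intervention and control groups on measures of knowledge scores, SURE top cores, CollaboRATE top scores". The next sentence begins "We examined acceptability of the intervention by looking at the usage of the DAs" and adds clinician satisfaction and perceived visit length. The section then states the test: "Differences between cohorts were examined using independent t-test (2-sided) for continuous variables".

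SDM Process is in neither the efficacy sentence nor the acceptability sentence.

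**The concern.** The Purpose section names two aims, efficacy and acceptability. A scored patient measure with a clear better direction and an assigned test would be expected to serve one of them, and SDM Process is placed under neither. The omission stands out because the worksheets exist to support shared decision making and this scale scores it directly.

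If the efficacy sentence were read as a closed list, an efficacy statement could rest on knowledge, SURE and CollaboRATE and pass over SDM Process whichever way it came out. A reader starting from Design would expect it to count. The document is dated June 2023, the survey was given from February to April 2019, and the text is mostly in the past tense, so one may ask whether the list was settled before the results were known.

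**Working it through.** There is no sample size, power, alpha or event figure to reproduce, so the check is mainly a comparison of the lists.

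**Step 1: set the lists side by side.**

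| Measure | Test named in Design | Efficacy list | Acceptability list |
|---|---|---|---|
| Knowledge | t-test | yes | no |
| SURE top score | Chi-square | yes | no |
| CollaboRATE top score | Chi-square | yes | no |
| SDM Process | t-test | no | no |
| Treatment preference | Chi-square | no | no |
| Worksheet usage | none | no | yes |
| Clinician satisfaction | none | no | yes |
| Perceived visit length | none | no | yes |

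Design tests five measures and the efficacy list holds three of them. That leaves 5 - 3 = 2 without a role: SDM Process and treatment preference. Treatment preference has no better or worse direction, so its absence from efficacy is unremarkable.

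**Step 2: ask whether two efficacy sets conflict.** They do not. Design says which test goes with which variable and includes treatment preference, so it cannot be read as a list of efficacy measures. Only Statistical Methods lists efficacy measures. The gap is an unstated role.

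**Step 3: ask whether an analyst would be stuck.** The score range and direction are in Measures, and the two-group t-test is in Design. Statistical Methods repeats a two-sided t-test for continuous variables and makes between-group differences in decision-making metrics a task of the study. SDM Process is plainly such a metric. The categorical test is named differently in the two sections (Chi-square and Fisher's exact), but that is a separate matter and does not touch this scale.

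**Step 4: ask whether list membership changes a result.** The document gives no primary outcome, significance level, multiplicity rule or definition of success, and says no power calculation was done. Nothing is computed from the efficacy list as a set.

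The precision of the SDM Process comparison illustrates this. The 95% half-width is t(0.975, 2n - 2) × SD × √(2/n). The document gives neither n nor SD. Assuming SD 1.0 and 25, 50 or 100 per group, the half-width is 0.569, 0.397 or 0.279 points on the 0-4 scale. The heading under which the measure is listed does not enter the formula.

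Only a rule that counted any one favourable result as efficacy would make list length matter. Assume two-sided 0.05, independent tests and no true differences. The chance of a false claim would then be 1 - 0.975³ = 0.073 for three measures and 1 - 0.975⁴ = 0.096 for four. The plan contains no such rule, and if it did, adding SDM Process would raise the error rate. These figures do not measure harm from the omission.

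**The case for a change.** The strongest case for a change is that the general phrase about decision-making metrics names no measure, while the sentence that names the efficacy measures leaves out the one nearest to the intervention's purpose. A slip in that sentence is still a slip, correcting it costs a few words, and a document written after the survey cannot show that the set was fixed in advance.

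Part of this stands. The role is unstated, and the document cannot rule out that the list was shaped after the data were seen. Neither point leads to a useful change:

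- The efficacy sentence has a typing error and no conjunction before its last item, which fits a dropped final entry better than a deliberate exclusion.
- SDM Process is named as a tested outcome in Design, so any reader could see if its result were not reported.
- The three listed measures are not blind to shared decision making. CollaboRATE asks whether what matters to the patient entered the choice, and SURE asks about clarity of values and support.
- Assigning a role now would not show what was intended in 2019. Without evidence of the original intent, it would itself be a decision made after the data were collected.

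Confidence intervals and an exploratory label are sound reporting practice for an unpowered pilot, but they apply equally to every measure here and do not depend on this omission.

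**Conclusion.** The omission is real but minor, and no change to the plan is needed. The roles of SDM Process and treatment preference are not written down. The test and its sidedness for SDM Process are, and so are its scoring and direction. Placing it in the efficacy sentence would alter no data, test, estimate or interval, so the numerical size of the issue is zero.

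This rests on two assumptions: that the SDM Process comparison is reported alongside the others, as Design implies, and that no success rule exists outside the document under which membership of the efficacy list would decide a claim. An analyst would sensibly treat SDM Process as one more between-group decision-making outcome in an unpowered pilot.
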